18.0 Provisions to Monitor the Data to Ensure the Safety of Subjects

- 18.1 The surveys/questionnaires/interview/focus groups will ask questions about satisfaction with and comfort of a new and traditional prosthetic harnesses and function skills. The study is not enrolling new amputees who have never been fitted for a prosthesis. We do not anticipate that these questions will be unsettling but should a subject need counseling or other assistance, the study will be completed in a medical environment with a physician specializing in amputation on the team. Resources will be readily available for counseling or other assistance referrals.
- 18.2 N/A. This research does not involve more than minimal risk to subjects.

19.0 Provisions to Protect the Privacy Interests of Subjects

- 19.1 Subjects will be interacting with the research and clinical teams, both comprised of licensed clinicians (physiatry, prosthetics, occupational therapy). The clinical team is the subjects standard care team. The research team is at the JAHVH. Should a subject not want to interact with one of the research team members, the situation will be discussed at a research team meeting. It may be necessary to unenroll the subject. Limits placed on to whom the subjects provide personal information will be honored. The licensed occupational therapist program manager who will be collecting data has extensive amputation, prosthetic, and research experience and has regularly received VA recognition for her empathy with Veterans.
- 19.2 The research team is permitted to access any sources of information about the subjects because they are VA employees.

20.0 Compensation for Research-Related Injury

20.1 N/A. The research does not involve more than minimal risk to subjects.

21.0 Subject Costs and Compensation

21.1 The only cost that will be incurred is travel to the VA. We are able to reimburse travel expenses (mileage, airfare, meals, hotel, etc.) for the subject and caregiver (if necessary). The Brasthesis harness will be provided at no cost to the subject.

- 21.2 Other than travel, no payments will be made to subjects.
- 22.3 The VA Medical Center is not responsible for any research-related injury treatment costs of a non-Veteran. The non-Veteran and his or her insurance or third-party payer cannot be a responsible party.

22.0 Consent Process

22.1

⊠Obtaining Signed Consent (Subject or Legally Authorized Representative)	□Obtaining Consent Online (Waiver of Written Documentation of Consent)
□Obtaining Signed Parental Permission	☐ Obtaining Verbal Consent (Waiver of Written Documentation of Consent)
☐Obtaining Signed Assent for Children or Adults Unable to Consent	
☐Obtaining Verbal Assent for Children or Adults Unable to Consent	□Waiving Assent/Assent is Not Appropriate

22.2 Informed consent process:

- The consent process will most likely take place over the phone. Potential subjects
 will contact the project manager who will answer questions and mail a blank
 informed consent for review. The potential subject will have up to one week to
 sign the consent and return the project manager in the provided addressed and
 postage paid envelop.
- If the potential subject has not responded within two weeks of mailing the blank consent document, the project manager will call the potential subject to answer further questions.
 - o The project manager and the PI will be involved in the consent process.
 - There will be no limit on the time devoted to the consent discussion.
 - The informed consent document itself and the person obtaining informed consent will explain that participation is voluntary and that they have the option of trying the Brasthesis harness or continuing to use their traditional harness.
 - The project manager obtaining informed consent is a licensed clinician with years of experience treating patients, responding empathetically, reading body language, creating an environment where patients feel safe to ask questions.
- 22.3 N/A. We will not be obtaining consent online or verbally.
- 22.4 Justification was provided in 17.5.
- 22.5 N/A. We will not be obtaining consent from non-English speaking subjects.
- 22.6 N/A. We will not enroll individuals who have not attained the legal age for consent.

22.7 N/A. Project does not involve HUD.

23.0 Setting

23.1 All research procedures will be performed at the JAHVH. Fitting of the Brasthesis harness may take place at other VA facilities via VideoConnect with the JAHVH-based research team and the subjects' home clinical team.

Brasthesis[™] Prototype for Women Veterans with Upper Limb Amputations

NCT ID: NCT05179395

IRB ID: STUDY003630 IRB Approval Date: 02/10/2022

Data Collection and Analysis

Aim 1. After signing of informed consent and during the same phone conversation as configuration of the bra order, the project manager will administer the baseline measures and obtain demographic and clinical data not available in the Computerized Patient Record System (CPRS). See Table 1. *The project manager will ask how many days per week and hours per day the participant wears their prosthesis with traditional harness (Aim 1, Research Question (RQ) 1.1)*. The project manager will explain, as delineated in the informed consent document, that she will contact the participant weekly during the fourweek wear phase for the purpose of tracking *Brasthesis*[™] wearing time. We will also employ an activity tracker as a quantitative proxy of prosthesis wear time. Similar systems have been employed in other prosthesis studies [20, 21] and the software provides direct export of accelerometer data to approximate wear time to the hour of each day. Participants will be provided a activity tracker by the prosthetist once the prosthesis has been successfully fit using Brasthesis[™]. The pre to post change ordinal data will be analyzed using quantitative descriptive analyses.

Other outcomes with valid and reliable measures include: satisfaction, measured with the Orthotic Prosthetic Users Survey (OPUS) Satisfaction with Device Scale [22] (Appendix 4), function, measured with the OPUS Upper Extremity Functional Status Scale [22] (Appendix 5) and comfort, measured with the Socket Comfort Score [23], a numeric rating 0-10 scale where 0 is the least comfortable and 10 the most comfortable). See Appendix 6 for our initial data coding plan. The pre to post change ordinal data will be analyzed using quantitative descriptive analyses. The results will be tabled and graphed.

At the end of the four-week wearing period, PI will conduct semi-structured *group* interviews (Aim 1, RQ 1.5) with the participants and fitting prosthetic team for the purpose of improving the fitting process. *The semi-structured interview will have three overall discussion points: (1) barriers encountered while fitting Brasthesis* TM, (2) *the strap placement prosess taking into consideration the presence and length of the residual limb and the available skin surface area available for contact with the prosthetic sensor, and (3) comparison of Brasthesis* TM *with traditional prosthesis*. Interviews will be tape recorded and transcribed. The text interview data will be analyzed using qualitative descriptive methods [24] based on the phenomenology framework [25] which is well suited for patient experience of care analyses. The first interview (first participant) will be coded line by line so that initial codes come from the data rather than pre-selected codes. The initial codes of the first interviews. Once all five interviews have been coded, the codes will be organized into themes. Interview data will be analyzed descriptively [24, 25].

Also at the end of the four-week wearing period, the activity trackers will be removed from the prosthesis by the prosthetist. Data will be downloaded by the prosthetist and engineer. Data will be analyzed descriptively and tabled and graphed.

Table 1 Variables					
Variable	RQ	Definition	Source, Timepoint		
Outcomes					
Wearing time	1.1	Days/week, hours/day, Traditional versus Brasthesis™	Weekly communication		
		activity tracker	Automated		

Satisfaction	1.2	OPUS Satisfaction with Device [22] (Appendix 4)			
Function	1.3	OPUS UE Functional Status [22] (Appendix 5)	Traditional – pre		
Comfort	1.4	Socket Comfort Score [23], 0-10 numeric rating scale	brustilests - post		
Barriers	1.5	Described by participants and clinicians	Post interview (QL)		
Pressure	2.1,2.2	Tekscan F-Socket (Appendix 7)	Prosthetist, engineer, post		
Demographic and Clinical Variables					
Age	All	Age on date of baseline data collection			
Sex		Male, female, other			
Race/ethnicity		Caucasian, African American, Hispanic, other			
Time since		In years: index event – date at baseline collection	CPRS, baseline		
Amputation level		transhumeral, shoulder, interscapulothoracic			
Prosthesis type		Myoelectric, hybrid, cosmetic			
Bra size		Size of She-fit® bra ordered			
OPUS=Orthotics and Prosthetics User's Survey, UE=upper extremity, QL=qualitative, CPRS=Computerized Patient Record System					

Aim 2. An effective harness must help hold the prosthetic socket securely on the limb, facilitate a functional range of motion, and remain comfortable when worn [26]. Therefore, on the day of the post wearing period group interview, we will perform a series of quantitative tests to characterize how Brasthesis [™] affects key biomechanical measures related to prosthesis fit, function, and comfort. We will first quantify the functional range of motion participants can achieve while wearing Brasthesis [™] and their conventional prosthetic harness. Movements relevant to upper limb prosthesis use such as maximum shoulder flexion/extension and abduction/adduction values [27] will be captured using goniometers and these values compared across both harnessing systems. As Brasthesis [™] is designed to accommodate female anatomy, we anticipate it will not encumber range of motion when compared to a conventional harness and likely even improve it.

Prosthesis fit, suspension, and comfort are three factors that are directly related to the pressure distribution developed at the interface between the prosthesis and the user's body [15, 28]. We will characterize pressure distributions when participants wear Brasthesis TM and their traditional harnesses. Following our previous work [15], we will employ a Tekscan VersaTek system that allows for measurements of pressures at two simultaneous locations across the body. We will quantify pressure development between the prosthetic socket and residual limb to characterize socket fit and changes in suspension, as well as around the contralateral axilla, an area that often bears prosthetic related loads and is commonly associate with discomfort in female prosthesis users. At each location, a Tekscan 9811E sensor will be used which is a "paper thin," flexible sensor, that can be trimmed to match anatomical contours and provides 96 discrete pressure measurements. Following our existing protocols [5] and prior to participants donning their prosthesis, we will adhere sensors using double sided adhesive tape directly to the skin to securely cover each participant's residual limb and in the contralateral axilla region. Using our existing laser scanner, we will create a 3D map that registers the location of each pressure sensor on the anatomy of the participant. Participants will then don their prosthesis and BrasthesisTM (or traditional harness) and Pressure measurements will then be performed following our previous protocols in which, (1) prepressure will be measured wearing the prosthetic liner with the residual limb

positioned neutral at their side, (2) wearing prosthesis with 90 degrees prosthetic elbow flexion, and (3) full elbow extension with shoulder flexion in the plane of the scapula [5].

Using MATLAB and Paraview software, we will import the sensor placement data and the pressure measurement data to create color-coded 'heat maps' that directly link pressure values to the three-dimensional anatomy of each participant. Using threshold filters and numerical integration we will isolate regions of particular interest (ex. regions where control electrodes must firmly contact the tissue), as well as regions developing maximum pressures, and calculate their surface areas. For each participant we will compare the maximum and mean pressures, the anatomical regions developing these values, and the surface areas which they are distributed across when wearing Brasthesis ™ compared to their traditional harness. We anticipate that the design of Brasthesis ™ will more equally distribute pressure across the contralateral axilla and thorax regions over larger surface areas. We further anticipate seeing minimal differences in pressure maps between the socket and residual limb indicating little change in prosthesis suspension.

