The term 'socket fit' encompasses the factors that impact prosthetic comfort and stability on the residual limb [15]. Fit and associated comfort have a substantial effect on user satisfaction and prosthetic use [15]. The socket is the crucial junction where the soft tissue of the user's residual limb interfaces with the rigid materials of the prosthesis. Socket fit must, for our purposes, accommodate the female anatomy as well as position the prosthetic device to efficiently transmit intended movements [15]. Socket fit also includes appropriate distribution of pressure across the residual limb. While compression can increase mechanical stability, it can also cause discomfort, tissue irritation, and damage. This challenge is increased for individuals with proximal amputations as the weight of the prosthesis amplifies the demand of the socket and the residual limb [15]. We believe that BrasthesisTM may relieve uncomfortable pressure at the residual limb by increasing the contact area of the harness to include the sports bra. The Revolutionizing Prosthetics 2009 program [16] offered a solution similar to BrasthesisTM to the problem of the tightening around the intact shoulder required by the traditional harness [16]. Recognizing that secure attachment to the body and distribution of weight are critical to comfortable fit and function, designed a shoulder-level socket with full fabric, tee shirtlike suspension.

Socket Pressure.

Accuracy and repeatability of the Tekscan F-Socket has been shown to be accurate with good reliability [17]. Daly et al. [18] were perhaps the first to use the pressure mapping with upper limb amputation research. No correlation was found between patient report of discomfort and pressure data. Schonfield et al. [15] built on the limitations of the Daly study to successfully characterize pressure distribution patterns unique to the participants socket designs. While using pressure mapping to better understand socket-fit is in its early stages, we believe that pressure mapping may be a useful tool to compare harness and socket pressure when wearing BrasthesisTM with the traditional prosthesis. We are not using pressure mapping to measure absolute values, rather, our focus is on how the harness distributes pressure and positions the socket on the residual limb and

thus influencing pressure distribution. [name] will provide expertise on pressure mapping on the proposed project

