4.0 Safety Endpoints

4.1 Primary endpoints are satisfaction, function, and comfort.

The secondary endpoints are the interface pressure that drives comfort and range of motion that drive functional movement.

Page 7 of 18 Revised: July 6, 2023

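### SAP Aim 2 compares pressure levels and thresholded areas with no stated correction, no stated use of the prepressure reading and no measure of evenness, although the question asked is about distribution

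*SAP*

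**What the plan says.** **Purpose.** Protocol section 3.0 (Socket Pressure) states: "We are not using pressure mapping to measure absolute values, rather, our focus is on how the harness distributes pressure". The same paragraph says that "pressure mapping may be a useful tool to compare harness and socket pressure when wearing" the new harness and the traditional prosthesis, so a comparison is intended.

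**Analysis.** SAP Aim 2 first filters the maps: "Using threshold filters and numerical integration we will isolate regions of particular interest". It then sets out the contrast: "For each participant we will compare the maximum and mean pressures, the anatomical regions developing these values". The extent of skin over which those pressures are spread is compared as well. It predicts a more even spread over the axilla and thorax, and little change between socket and residual limb. It gives no threshold value, does not say whether the threshold is absolute or relative, and mentions no zeroing, calibration or normalisation.

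**Prepressure.** Both documents list it as the first of three recordings: "prepressure will be measured wearing the prosthetic liner with the residual limb" in neutral position. Neither says what it is for. In the SAP, the list follows a sentence in which the participant puts on the prosthesis and harness; protocol section 6.0 gives the list without that sentence.

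**Timing.** Protocol section 6.0 maps the traditional harness at the fitting visit and Brasthesis after the four-week wearing period. SAP Aim 2 places the tests on the day of the post-wear interview, apparently for both harnesses.

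**The concern.** The pressure endpoint is a within-person contrast between two recordings in five women, analysed descriptively and without a control group. Anything that shifts one recording and not the other goes straight into that contrast, and there is little to average it out or expose it.

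The sensors are trimmed by hand and taped to the skin. Under the protocol's schedule the second application comes at least four weeks after the first. A different zero level or sensitivity is then possible, and the text describes no step to remove it.

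The SAP's main expectation is about evenness. Maximum, mean and a thresholded area do not measure evenness directly, and all three move when the level of the whole map moves. The opposite expectation, little change at the socket, could be falsely refuted or falsely supported in the same way.

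**Working it through.** The plan contains no figure to reproduce: no hypotheses are tested, and the five completers have no stated derivation. The check is therefore of the mechanism.

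**Inputs from the documents.** 96 readings per sensor (SAP Aim 2); two recordings per woman; compared quantities are maximum, mean and thresholded area.

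**Assumptions, not in the documents.** One skewed pressure pattern, identical under both harnesses, so the true effect is zero. Mean 20 and maximum 66.24 in arbitrary units; coefficient of variation (CV) 0.586. Fixed area threshold 30, which 15 cells exceed. Prepressure contains the offset only. Offset and gain are common to all cells of a sensor.

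**Model.** Reading = gain × pressure + offset. The first recording has gain 1 and offset 0.

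| Second recording | Mean | Maximum | Cells above 30 | Peak/mean | CV |
|---|---|---|---|---|---|
| Offset 2, gain 1 | 22 (+10%) | 68.24 (+3%) | 21 (+40%) | 3.102 (−6%) | 0.533 (−9%) |
| Same, prepressure subtracted | 20 (0%) | 66.24 (0%) | 15 (0%) | 3.312 (0%) | 0.586 (0%) |
| Offset 0, gain 1.1 | 22 (+10%) | 72.86 (+10%) | 22 (+47%) | 3.312 (0%) | 0.586 (0%) |
| Offset 2, gain 1.1 | 24 (+20%) | 74.86 (+13%) | 24 (+60%) | 3.119 (−6%) | 0.537 (−8%) |
| Same, prepressure subtracted | 22 (+10%) | 72.86 (+10%) | 22 (+47%) | 3.312 (0%) | 0.586 (0%) |

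1. **Offset.** The mean is 20 + 2 = 22. Peak/mean falls from 66.24/20 = 3.312 to 68.24/22 = 3.102. The map looks more even although nothing changed, which is the result the SAP predicts. Subtracting prepressure removes this.
2. **Gain.** The mean is 1.1 × 20 = 22. Subtraction does not help; a ratio does, because 72.864/22 = 66.24/20.
3. **Both.** Subtraction leaves +10% in the mean. Subtraction followed by a ratio leaves 0%, so both steps are needed.
4. **Relative threshold.** A cut at 1.5 × the map's own mean is 30 in the first map. After subtraction with gain 1.1 it is 1.5 × 22 = 33, and 1.1p > 33 is the same condition as p > 30. The count stays at 15.
5. **Range.** Over offsets 0 to 4 and gains 0.95 to 1.2, the uncorrected mean moves by −5% to +40%, and the subtracted mean by −5% to +20%.
6. **Error shared by both recordings.** With a true 10% reduction and offset 2 in both, the means are 22 and 18 + 2 = 20. The difference is −2.0, as without the offset; the percentage is −2/22 = −9.1% instead of −10%. No false effect arises.
7. **Limit of relative measures.** A uniform 10% reduction gives 59.616/18 = 3.312, so peak/mean cannot see it.

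**The case against.** The strongest reply is that this is thin reporting and not a faulty analysis. Four parts of it stand.

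- **Silence is not absence.** A reader might infer that raw readings will be analysed and that prepressure is never used. The documents do not support this. The SAP says measurement follows the team's earlier protocols, which are not reproduced and may include zeroing and calibration. What can be said is that no correction and no use are stated.
- **No flat contradiction.** A reader might infer that the SAP breaks the protocol's promise. It does not: a within-person contrast is a relative use of the readings, the protocol intends a comparison, and the SAP compares regions and areas as well as levels.
- **The error must differ between recordings.** Step 6 shows that a shared error does no harm. The protocol's Background calls the sensor accurate with good reliability. If both harnesses are mapped on one day with one sensor application, the risk is smaller. The SAP does not say that one application serves both.
- **Level matters too.** Replacing maximum and mean with relative measures would hide a uniform pressure reduction. The SAP also cares about firm electrode contact, which is a matter of level.

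A reader might also set "The secondary endpoints are the interface pressure that drives comfort" (protocol 4.1) against "No correlation was found between patient report of discomfort and pressure data" (Background) and infer that pressure will be used to conclude about comfort. No analysis step does so. Comfort has its own measure, the Socket Comfort Score, and the null result comes from one early study. The wording in 4.1 merits a minor edit at most and is not part of this point.

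The reply does not remove the missing evenness measure, the unstated role of prepressure, the unspecified threshold or the timing conflict.

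**Conclusion.** The point holds as a gap that is cheap to close. As written, SAP Aim 2 would carry any between-session difference in offset or gain into maximum, mean and area (if the threshold is fixed), and it has no summary that directly answers its own question about evenness.

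The size is not known. The percentages above rest on assumed errors and an assumed map; they show direction and relative sensitivity, not what this system will do. Thresholded area was the most sensitive quantity, although it is the SAP's closest link to distribution. The cancellation by relative measures assumes one gain for the whole sensor.

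How serious this is depends on the schedule: it is plausible under the protocol's two sessions and weaker under same-day testing. Pressure is a secondary endpoint in a descriptive series, so no error rate or sample size is affected.

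**What to change.** In SAP Aim 2:

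1. State that prepressure is recorded with the liner on, before the prosthesis and harness are donned. Subtract it cell by cell from positions 2 and 3 for each harness. Show unsubtracted values alongside, because subtraction also takes out real liner pressure and corrects offset only.
2. Add the peak-to-mean ratio and each predefined region's share of total load, computed within each sensor location. Set the area threshold relative to each map's own mean or maximum. Base any conclusion about a more even spread on these relative measures.
3. Keep maximum and mean pressure as reported comparisons.
4. Reconcile the timing of the two harness recordings between protocol section 6.0 and SAP Aim 2, and state whether sensors are reapplied between them.

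Cost: SAP wording, a few lines of analysis code, a few more summaries per participant and slightly noisier subtracted values. No new data are needed.
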